## **6.2 Description of Evaluations**

Evaluations will occur at 5 points during the study: (1) Pre-Treatment Screening of Baseline Data, (2) Treatment enrollment, (3) Treatment Group 1 through 7, (4) Treatment closeout, and (5) Post-Treatment Follow-up Data. This schedule is summarized in the table above and a detailed description of each phase of the study is described below. The evaluations and timepoints described below in 6.2.2 and 6.2.3 are part of standard practice at CaringKind and collected universally as part of the V-CST treatment program. We will be accessing the information from these evaluations secondarily for our study.

### **6.2.1 Pre-Treatment Data Screening**

Pre-treatment data screening will be conducted first to determine which patients at each HCS are eligible for the study. These evaluations will be conducted by the HCSs examining their electronic health records to identify eligible participants based on the study's inclusion and exclusion criteria.

Eligible participants will be randomized at each site and allocated into either the control or intervention arms. At this time, the following data will be abstracted from HCS records on the eligible participants: ICD-10 code(s) for dementia; demographics; medications; and cognitive screening scores.

Participants randomized to the intervention arm will be referred for V-CST.

Pre-Treatment Data Screening will conclude with HCSs uploading the abstracted data to the project Sharepoint file.

### **6.2.2 Treatment Enrollment**

During V-CST enrollment, V-CST facilitators will conduct an orientation session for the intervention group and obtain clinical consent for participation.

### **6.2.3 Treatment Sessions**

Over the course of 14 treatment sessions in 7 V-CST groups, five process measures will be collected by the V-CST facilitators at each session:

- Patient attendance (percentage of 14 sessions attended)
- Protocol fidelity: CST protocol followed per Therapy Administration Form
- Attrition: Patient dropping out of V-CST group and stopping attendance
- Weekly Monitoring CST Participant Progress reports
- Adverse Events

V-CST will end after the 14 sessions (plus orientation and closeout sessions) and participants continue with their standard of care treatment at their HCS.

### **6.2.4 Post-V-CST Data Screening**

Post-V-CST data screening will be conducted by the referring physician after the 14 V-CST sessions have been held.

At this time, post-intervention data on medications and cognitive screening scores will be abstracted from HCS records on the study participants. Post-treatment data screening will conclude with HCSs uploading the abstracted data to the project Sharepoint file.

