### **Interventions and Duration**

Referral for V-CST is the intervention that will be introduced in the two participating sites. CST is an evidence-based group therapy that is recommended for people with a diagnosis of mild cognitive impairment and/or mild to moderate dementia and has been recommended by the United Kingdom's National Institute for Health and Care Excellence since 2006 (NICE, 2006, 2018). It is a version of cognitive stimulation developed from the theory of reality orientation, which has been supported from a Cochrane review in a pilot trial (Spector et al., 2001) and a full randomized control trial (Spector et al., 2003). Analyses showed that CST had benefits comparable to those of accepted pharmacological treatments for dementia and was cost effective (Knapp et al., 2006). Additionally, RCTs have shown CST to have significant beneficial impacts on quality of life (QoL) (Butler et al., 2020), depression (Stewart et al., 2017), and cognition (Aguirre et al., 2013), and CST has been found to be efficacious for those with Alzheimer's disease and vascular dementia (Piras et al., 2017). CST is increasingly accessible in practice internationally and even accessible to low-income countries (Spector et al., 2019).

CST is a structured cognitive intervention involving 14 thematic sessions that promote participants to engage in various activities and discussions. Each session is typically 45-minutes, and it is offered twice per week over a seven-week period (Spector, 2003). The CST protocol is clearly defined and has been adapted for online delivery as Virtual CST (V-CST) to support social distancing (Cheung & Peri, 2020). CST-trained facilitators will adhere to the CST training manual, which outlines the 14-themed sessions and itinerary for each session (Appendix A), and will deliver the therapy online. The study duration will occur over 1 year starting with screening by the physicians at the two HCSs and end when data analysis is completed. The participants will be involved in the research protocol for up to 1 year from the start of the referral process to the end of the follow-up visit with their referring physician.

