### **Sample Size and Population**

The target population is people with mild cognitive impairment and/or mild to moderate dementia, and the study population will include those who are English-speaking and web users from one of the two health care system sites. 168 study participants will be enrolled into the study; 56 participants will be randomly assigned to the intervention group (V-CST referral) and 112 participants will be allocated to the control group to receive the current standard of care (no V-CST referral).

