#### **Intervention Group only:**

Minimal risks to PLWD are expected and no Adverse Events (AEs) or Serious Adverse Events (SAE) of CST have been reported in over 15 years of studies. The minimal risk of participation in CST has been established through implementation of CST in numerous studies and countries, as an international CST implementation research study protocol summarizes: “CST has no documented adverse effects and, therefore, risk to participants will be low” (Spector et al., 2019). Despite the established low risk for any AEs or SAEs, our stakeholder engagement processes include attention to risk minimization, including the risks of in-person treatments posed by the COVID-19 pandemic. To eliminate these risks, CST will be delivered online in this trial. The team’s experience delivering CST online has further confirmed the dearth of risks from participating in CST. There is a risk for breach of privacy. To address the risk for breach of privacy, participants will be encouraged to attend virtual sessions in a private setting. However, due to the nature of a virtual setting, the facilitators cannot guarantee privacy. Additionally, the V-CST site will follow standard of care protocol and HIPAA compliance policies within their institution to protect participant privacy. Finally, subjects will be in group therapy and already identified by everyone else in the group. This breach in privacy is not feasibly avoidable due to the nature of the therapy. This breach in privacy will be reviewed and discussed during the clinical assent process. Finally, a potential risk for this patient population is increased stress related to the virtual aspect of the intervention. To mitigate this risk, the facilitators created and implement an orientation prior to beginning V-CST.

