## **5 STUDY INTERVENTIONS**

### **5.1 Interventions, Administration, and Duration**

The intervention introduced in the pilot pragmatic trial is V-CST referral by physician. V-CST referral will be provided to 56 patients who are randomly allocated to the intervention group. CST is an evidence-based group therapy that is recommended for people with a diagnosis of mild to moderate dementia. In this study, CST will be delivered online via Zoom and referred to as virtual CST (V-CST). CST is administered twice weekly over a seven-week period for a total of 14 sessions. At each group session, there will be a total of up to eight participants, and the sessions typically last between 45 minutes to 1 hour and are co-facilitated by two CST-trained facilitators from CaringKind: One facilitator leads the V-CST sessions (lead facilitator), while the other provides participant support (facilitator). To help with adherence rates, reminder emails are sent to participants on the morning of the session, and adherence is captured by CaringKind recording participant attendance at each session per standard of care.

Facilitators ensure privacy and protect safety by providing password protected Zoom sessions. A meeting password is required, and the 'waiting room function' is used to ensure that only those who are intended to join the meeting are admitted.

**Adverse effects:** Some people with dementia may have difficult or traumatic memories, and sensitivity is required not to push group members into sharing painful memories. Additionally, current affair discussions involve topics that members may find uncomfortable to discuss. To mitigate these events, the group members will be able to choose from a list of topic discussions. However, should a participant become upset during the discussion, the facilitators will determine if the person can remain in the group; if the participant is unable to remain in the group (e.g., due to uncontrolled anger), the facilitator will remove that participant from the group to provide him or her private space to discuss what happened. The lead facilitator will inform the HCS of adverse events. Facilitators will respond to adverse events per their SOC protocol at CaringKind. Adverse events will be reported to the HCS clinicians following reporting

guidelines detailed below in section 7. Topics that elicit such events will be removed from the V-CST protocol.

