## **7.3 Adverse Events and Serious Adverse Events**

Definitions for adverse events (AEs), serious adverse events (SAEs), and Unanticipated Problems (UP) to be used for this trial are provided below:

**Adverse Event (AE):** Any unfavorable medical occurrence in a clinical research study participant, including any abnormal sign (e.g., abnormal physical exam or laboratory finding), symptom, or disease, temporally associated with the participants’ involvement in the research, whether or not considered related to participation in the research.

**Serious Adverse Event (SAE):** Any adverse event that:

- Results in death,
- Is life threatening, or places the participant at immediate risk of death from the event as it occurred,
- Requires or prolongs hospitalization,
- Causes persistent or significant disability or incapacity,
- Results in congenital anomalies or birth defects,
- Is another condition which investigators judge to represent significant hazards.

**Unanticipated Problems (UP):** Any incident, experience, or outcome that meets all of the following criteria: unexpected, in terms of nature, severity, or frequency, given (a) the research procedures that are described in the protocol-related documents, such as the IRB-approved research protocol and informed consent document; and (b) the characteristics of the study population; related or possibly related to participation in the research; suggests that the research places participants or others at a greater risk of harm (including physical, psychological, economic, or social harm) than was previously known or recognized.

As stated above, one possible AE for this study is increased stress. For example, it is possible that the group discussion that takes place will increase participant stress. Increased stress is a possible mild AE of CST. This study has no other AEs.

No SAEs are expected. No AEs or SAEs of CST have been reported in over 15 years of studies. CST involves group discussions, and in this trial, CST will be delivered online to prevent infectious disease transmission.

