Although hospitalizations and death or not uncommon in this population in general, they are unlikely to be related to the study. In the event of hospitalizations or death of V-CST participants identified by the V-CST facilitators, the lead facilitator will report this information to the referring physician per standard of care practice. In the event of hospitalizations or death of any study participant (intervention or control group) identified by the referral site, the referral site will report this information to the study coordinating site (UMass).

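### The post-treatment record pull covers every randomized participant but omits deaths and hospitalizations, so the safety summaries may be incomplete and cannot support an unbiased comparison by arm

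*Combined protocol and SAP*

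**What the plan says.** **Scope.** Section 7.3 defines an AE broadly, by timing relative to "involvement in the research, whether or not considered related to participation in the research". Section 11.2 places enrollment at randomization, so controls and people who decline the referral are in scope.

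**Scheduled collection.** Section 6.2.3 states that "five process measures will be collected by the V-CST facilitators at each session", and AEs are one of the five. Section 7.2 has facilitators watch for harm while therapy is being delivered. The schedule in Section 6.1 marks AEs only in the treatment column (Day 0 to 200). Under Section 7.3.1 the lead facilitator starts the AE form, and the AE metric in Section 10.3.3 is summed over V-CST participants.

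**Deaths and hospitalizations.** Section 7.3 has two routes. Facilitators pass on events they learn of in V-CST participants to the referring physician. For any participant in either arm, events "identified by the referral site, the referral site will report this information to the study coordinating site (UMass"). Section 7.3.1 adds that facilitators and referring sites will assess these events.

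**Record pull.** Section 6.2.4 says that "post-intervention data on medications and cognitive screening scores will be abstracted from HCS records on the study participants". The field lists in Sections 7.4 and 10.2 contain no death or hospitalization item.

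**Reporting.** Section 7.3.1 sends the Safety Officer periodic summaries of all AEs, serious AEs, deaths and unanticipated problems. No breakdown by arm or denominator is stated.

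**The concern.** The duty to report covers everyone randomized, but the only scheduled collection of AEs is in those who attend V-CST. For deaths and hospitalizations, neither route comes with a search method, a time point or a record source. Attendees have an advantage all the same: facilitators see them twice a week, and Section 9.42 has the delivery team email anyone who misses a session to ask why. If someone stops attending, the clinic is told and asks about it at the next visit. Controls and decliners have no counterpart to this.

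Two things are at stake. First, completeness: an event that nobody happens to notice never reaches the summaries. Second, comparability: if anyone splits the counts by arm, part of any difference will be detection. The summaries carry more weight than usual because Section 7.3.1 classes all deaths and hospitalizations in advance as expected and unrelated. The expedited routes are for unexpected events, so the periodic summary is where an imbalance would have to show. Section 7.3 itself accepts that such events are not uncommon in this population.

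**Working it through.** The documents give no event rate, detection rate or safety sample size, so there is no figure of the plan's own to reproduce. The check has two parts.

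**1. Who is covered by what**

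| Source | V-CST attendees | Controls and decliners |
|---|---|---|
| AE collection at sessions (6.1, 6.2.3, 7.2) | yes | no |
| Query after a missed session (9.42) | yes | no |
| Referral-site notice of death or hospitalization (7.3, 7.3.1) | yes, passive | yes, passive |
| Post-treatment record pull (6.2.4, 7.4, 10.2) | no field | no field |

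The last row is the only one that is systematic and common to both arms, and it leaves these events out.

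**2. How large the distortion could be**

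Inputs from the documents:
- Arm sizes (Sample Size and Population): "56 participants will be randomly assigned to the intervention group (V-CST referral) and 112 participants will be allocated to the control group".
- Treatment period (Section 5.1): "CST is administered twice weekly over a seven-week period for a total of 14 sessions", that is 7 x 7 = 49 days.
- Follow-up (Interventions and Duration): "The participants will be involved in the research protocol for up to 1 year", taken as 365 days. As an alternative, 275 days, the last day in the Section 6.1 schedule.

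Assumptions, none of them from the documents:
- True risk is equal in the two arms and constant over follow-up.
- The clinic route notices a fraction c of events in both arms, with c = 0.5 to 0.7.
- All 56 intervention participants attend, and facilitators catch every event in the 49 days. This favors a large gap.

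With f the share of follow-up spent in treatment, detection is c in controls and c + (1 - c) x f in the intervention arm. The apparent risk ratio is [c + (1 - c) x f] / c.

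| Follow-up | f | c = 0.5 | c = 0.7 |
|---|---|---|---|
| 365 days | 49/365 = 0.134 | 0.567/0.5 = 1.13 | 0.740/0.7 = 1.06 |
| 275 days | 49/275 = 0.178 | 0.589/0.5 = 1.18 | 0.753/0.7 = 1.08 |

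If only half of the intervention arm attends, f halves and the 365-day ratios fall to 1.07 and 1.03.

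In counts, take an assumed true risk of 20% over 365 days with c = 0.5. Controls would show 112 x 0.20 x 0.5 = 11.2 of 22.4 events. The intervention arm would show 56 x 0.20 x 0.567 = 6.4 of 11.2, against 5.6 with equal detection. The distortion is under one event. The shortfall is larger: (11.2 + 6.4)/33.6 = 52% of events reported.

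Incompleteness also weakens a reassuring result. Zero events among 112 controls gives an upper 95% bound of 1 - 0.05^(1/112) = 2.6% if detection is complete. At 50% detection the bound is 2.64%/0.5 = 5.3%.

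**The case against.** The best defense is that this is a minimal-risk feasibility pilot of a referral. No safety hypothesis is tested in Section 9.5, the summaries are not planned by arm, and the AE metric is already confined to V-CST participants. A both-arm route for deaths and hospitalizations exists. Section 10.2 deliberately limits the pull to selected fields, under consent and HIPAA waivers. All of this stands, and it limits the consequence. It does not supply a search method for either arm or make the summaries complete.

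Several stronger readings are tempting and should not be drawn:

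- *Deaths and hospitalizations are actively sought in attendees only.* No active search is described for attendees either. The contrast is between passive notice alone and passive notice plus facilitator contact.
- *Safety ascertainment ends at Day 200.* Only the AE row of the schedule ends there. The referral-site route has no end date, and the summaries run to the end of enrollment or data collection.
- *Controls have no contact.* Section 4.1 requires that a clinic visit be expected 6 to 12 months after record review for every participant.
- *The apparent risk ratio could be 1.3 to 1.8.* That follows if 90% of intervention events are noticed against 70% or 50% of control events. Setting c + (1 - c) x f = 0.9 gives f = 0.2/0.3 = 67% or f = 0.4/0.5 = 80%. So 67-80% of events would have to fall in a window that is 13-18% of follow-up.
- *AE collection must extend to orientation*, because Section 2.3 says that "a potential risk for this patient population is increased stress related to the virtual aspect of the intervention". The same section offers orientation as the mitigation, and Section 4.3 places it outside the study protocol.

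**Conclusion.** The concern holds in a limited form. Session AEs are single-arm data by design. Deaths and hospitalizations have a passive, undefined route in both arms, with an added source of notice for attendees. The one record pull common to all participants omits them. The Safety Officer's summaries may therefore miss events in either arm, and they cannot support an unbiased comparison by arm if someone makes one.

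The likely distortion is modest: an apparent risk ratio of about 1.06-1.13 over 365 days, or 1.08-1.18 over 275 days. This rests on clinic detection of 50-70%, equal and constant true risk, full attendance, and complete facilitator detection for 49 days. The last two push the ratio up. Clinic detection is the sensitive input: at c = 0.2 the formula gives (0.2 + 0.8 x 0.134)/0.2 = 1.54 over 365 days. That would mean clinics overlook four of five such events in their own patients, and incompleteness would then be the larger problem.

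The omission does not touch the H1 comparison itself. The change is worth making because it is cheap and specific.

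**What to change.** - In Sections 6.2.4, 7.4 and 10.2, add death (date) and hospitalization (yes/no, dates) to the post-treatment abstraction for all randomized participants, searched the same way in both arms from randomization to the follow-up pull.
- In the Section 6.1 schedule, mark this item in the post-treatment column.
- In the Section 7.3.1 summaries, report these counts with denominators by assigned arm.
- In Sections 7.3.1 and 10.3.3, label session-observed AEs as single-arm data, not to be set against control.

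A side benefit is that a death date separates death from other reasons for a missing cognitive score before the multiple imputation in Section 9.5.

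The cost is slightly more abstraction per participant and a small amendment to the data-element list under the existing waivers, with IRB review. The Section 2.3 statement that no sensitive information is collected should be reread at the same time. Events outside the record system may still be missed, but the method of looking will be the same in both arms.

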## **7. SAFETY ASSESSMENTS**

This study is of minimal risks, and there are no known risks to participants in the proposed trial. Furthermore, online delivery of CST adheres to COVID social distancing guidelines keeping this vulnerable population safe. Currently, memory clinics do not standardly provide non-pharmacological interventions to their patients, so no alternative treatments will be provided besides V-CST.

Minimal risks to participants are expected, and no Adverse Events (AEs) or Serious Adverse Events (SAE) of CST, V-CST, or referral for V-CST have been reported over the last 15 years. Numerous studies have established CST to be of minimal risks to participants and report: “CST has no documented adverse effects and, therefore, risk to participants will be low” (Spector et al., 2019). Despite the established low risk, our processes will mitigate the risk for in-person interventions by offering CST online.

No safety events are expected. A possible AE may be participant stress during a group discussion. Some people with dementia may have difficult or traumatic memories, and sensitivity is required not to push group members into sharing painful memories. Additionally, current affairs discussions involved topics that members may find uncomfortable to discuss. To mitigate these events, the group members will be able to choose from a list of topic discussions. Should a participant report or exhibit increased stress during participation in V-CST, two primary actions will be taken: First, the V-CST facilitator will try to address and reduce the participant’s stress, and if the participant is unable to remain in the group, the facilitator will remove that participant from the group to provide him or her private space to discuss what happened. Facilitators will respond to adverse events per their SOC protocol at CaringKind. The facilitator will inform the HCS of adverse events. Topics that elicit such events will be removed from the V-CST protocol.

